RCT Randomised Controlled Trial

REC Research Ethics Committee

SEWTU South East Wales Trials Unit

SOP Standard Operating Procedure

TMF Trial Master File

TMG Trial Management Group
TSC Trial Steering Committee

FILTER PROTOCOL v.3.0. 27.11.2014

1 Amendment History

Amendment No.	Protocol version no.	Date issued	Author(s) of changes	Details of changes made
1	2	13.10.14	AF	Trial manager updated (RP)
2	2	13.10.14	AF	Wording of Criterion 1 changed as recommended by TSC (p.26)
3	2	13.10.14	AF	DMC section updated as TSC agreed not required (p.35)
4	3	27.10. 14	AF; RP	Updated details throughout of the post-follow-up saliva testing sample size (n=200 reduced to n=192, 32 per FE setting and methods (cotinine and anabasine tests).
5	3	27.10.14	AF; RP	The methods for monitoring intervention team time spent on the Filter FE Challenge has also been updated (p. 29): "Detailed workload surveys emailed on a weekly basis to the core intervention staff will assess time spent on intervention-related tasks for each FE setting."
6	3.1	2.2.15	JW; AF	The definition of frequent cannabis use has been changed from 3 times to >=4 times in the past 30 days throughout the protocol. Cannabis use in the past 30 days has also been added as a secondary outcome.
7	4	11.2.15	AF; RP; BL	Student focus group numbers amended from 4 focus groups per intervention setting to 2 focus groups for sixth form, 4 focus groups for medium size college and 6 focus groups for large college (p.9; p.20)

[figure not shown]
2 Synopsis

Short title	Filter FE pilot trial
Acronym	Filter FE
Trial design	A pilot clustered randomised controlled trial (RCT) and embedded process evaluation of 'the Filter FE Challenge' to evaluate intervention and trial feasibility and acceptability.
Trial participants	The trial will involve six Further Education (FE) settings. New students aged 16-18 enrolling in September 2014 will be recruited to baseline and 1-year follow-up surveys. The process evaluation will include focus groups with students and staff, a brief survey of staff trained by the intervention team, interviews with institutional managers and the intervention team.
Planned sample size	Six FE settings will participate in the trial: 3 intervention group; 3 control group. The following diversity/matching criteria will be used to recruit six FE settings: 'sixth form' colleges attached to schools (n=2); small FE colleges/campuses (new intake fewer than 500) (n=2); large FE colleges/campuses (new intake more than 500) (n=2). New students aged 16-18 enrolling in September 2014 will be recruited to baseline and 1-year follow-up surveys. The estimated sample is 2500. No power calculation has been performed for this pilot trial as our primary aim is to evaluate feasibility and acceptability. A sub-sample of approximately 96 students will also be recruited across the three intervention sites (purposively by socio-economic status, gender, and smoking status) to participate in focus groups (2 focus groups for sixth form, 4 focus groups for medium size college and 6 focus groups for large college). To explore the validity of self-reported smoking measures and if this varies by arm, 192 students will be recruited immediately after the follow-up survey via stratified, random sampling to provide a saliva sample for cotinine and anabasine testing. Staff who participate in the training component will be recruited to take part in a brief post-intervention survey to explore their experiences of the process (approximately 70 in total; 10, 20, 40 per institution depending on size); a sub-sample of approximately 48 intervention college staff will also be recruited (purposively by gender and role) to participate in focus groups (n=2 per college). Two members of the senior management team at each participating FE setting (n=12) will be interviewed.
Follow-up duration	Twelve months
Planned trial period	Twenty-four months
Primary objective	This study aims to evaluate the feasibility and acceptability of implementing and trialling 'The Filter FE Challenge' and assess whether pre-specified feasibility and acceptability criteria are met prior to submission of a potential phase-III trial application.

Secondary objectives	To explore the experiences of FE students, staff and the intervention delivery team to refine the intervention and study design prior to a potential phase-III trial. To pilot primary, secondary and intermediate outcome measures and economic evaluation methods prior to a potential phase-III trial.
Primary endpoint	The intervention phase of the trial is expected to continue until July 2015.
Secondary endpoints	The follow-up survey will take place in September 2015 and the process evaluation will continue until November 2015. The trial will be considered to have ended in July 2016 (month 24) when the final report is submitted.
Interventions	The Filter FE Challenge.

3. Trial summary

3.1 Participant flow diagram

3.2 Trial summary

This study will examine the feasibility and acceptability of delivering and trialling 'The Filter FE Challenge' (a new smoking prevention programme designed for FE settings), including how this this varies according to institutional context; explore student, staff and intervention team experiences; and pilot primary, secondary and intermediate outcome measures and economic evaluation methods prior to a potential phase-III trial.

To facilitate this, researchers will work collaboratively with Action on Smoking and Health (ASH) Wales, who will recruit six FE institutions (four FE colleges and two 'sixth forms' attached to schools) to take part in the study. After institutional recruitment, new students

aged 16-18 enrolling at all participating FE settings for the 2014-15 academic year will complete a survey that will give information about smoking practices and attitudes. Two FE colleges and one school sixth form will be randomised post-baseline survey to the intervention group and will take part in 'The Filter FE Challenge' for the remainder of the 2014-15 college year (i.e. until July 2015). The other three institutions will act as a 'control' group and continue with normal practice. After 12 months a follow up survey will be conducted with the same cohort of students. We will also pilot collecting further information about the institutional and local neighbourhood environments (pre- and post-intervention) via observations, 'mystery shopper' audits of local shops, and an analysis of college policy documents.

At intervention sites, ASH Wales will provide project managers, education officers, social media experts and trained youth workers from The Filter team to help implement five new smoking prevention activities at intervention sites as described below:

- 1. The project manager will work with local retailers to inform them about the project and trading standard penalties for selling tobacco to under-18s.
- 2. The project manager will work with college staff to implement smoke-free policies on campus.
- 3. Education officers will train college staff to teach students about the harms of smoking and how to change their campus environment.
- 4. Existing web-based information, social media campaigns and on-line services designed for young people will be integrated with the college's website and social media.
- 5. Youth workers will provide credible messages about the benefits of not smoking and resisting pressure to smoke.

Information about student, staff and intervention team experiences will be collected through interviews with FE college managers, the intervention delivery team and in focus groups with intervention college students and staff.

From students who complete the follow-up survey, a subsample of 192 will be recruited to provide a saliva sample for cotinine and anabasine testing to examine the validity of the self-reported smoking outcome.

4 Introduction

4.1 Background

Smoking is a major cause of preventable illness, premature death and health inequalities in the UK. Preventing young people from taking up smoking is vital to maintain and accelerate recent declines in smoking rates. Although much research has been undertaken to develop and evaluate school-based prevention interventions targeting 11-15 year-olds¹, smoking continues to grow rapidly amongst older adolescents². With over 1.5 million British 16-18 year olds now enrolled in further education (FE) courses, new smoking prevention interventions are required that target FE settings (e.g. general FE colleges, 'sixth form' colleges attached to secondary schools, etc.)³. As well as being a period in the life-course when smoking often begins, the transition to FE itself can increase the risk of smoking as young people are exposed to new sources of peer influence and have more independence from their parents.

Research evidence about smoking prevention interventions delivered in FE settings is sparse. Two recent systematic reviews of health improvement interventions in educational sites^{4,5} contain no reference to such studies in FE settings. This finding supports recent calls from the National Institute of Health and Care Excellence (NICE)³ for more evidence regarding smoking prevention interventions in secondary schools and in other youth settings such as FE institutions. Furthermore, the failure of the two reviews^{4,5} to identify any cluster randomized controlled trials (RCTs) undertaken within FE settings highlights the lack of rigorous health improvement evaluation in this context to date.

A wider search of literature on smoking prevention in FE identified 14 relevant reports⁶⁻¹⁹. Amongst these, six non-systematic literature and policy reviews reported increasing policy interest in health improvement interventions targeting young people within FE settings but noted the absence of any evidence regarding appropriate or effective interventions in FE settings^{6,7,9,10,12,14}. No examples of effective smoking prevention interventions delivered in this context were identified. Three studies evaluated single-session motivational interviewing (MI) interventions in English FE settings^{8,11,17} finding that it is feasible to deliver brief interventions within FE settings¹¹. These studies also found that MI targeting high-risk students engaged in drug use may reduce their use of cigarettes, alcohol and drug use⁸. However, it was not an effective method for preventing the uptake of smoking among 16-19 year-olds in FE¹⁷. One quasi-experimental study of a multi-component intervention combining health education, counselling and nicotine therapy in French vocational colleges was found to be effective in supporting smoking cessation¹⁹.

With no evidence of effective smoking prevention methods or approaches in FE settings, five recent systematic reviews of smoking prevention interventions delivered in other educational and/or community contexts were identified and consulted to inform intervention development²⁰⁻²⁴. The reviews suggest the following evidence-based smoking prevention

FILTER PROTOCOL

methods and approaches are effective: reducing the illicit sale of tobacco products to under-18s²⁰⁻²³; initiating tobacco-free policies and environmental change²²; age-appropriate, interactive educational messages delivered via intensive, long-term mass media campaigns²¹; and social competency and skill development interventions to support young people to resist peer influence²⁴. A recent systematic review of school effects/environment interventions also found that initiating tobacco-free policies and environmental change is effective, especially in permissive contexts⁴ which is likely to be the case in some FE settings.

Such knowledge highlights the relevance of multi-level smoking prevention interventions and identifies a set of intervention techniques and functions that may underpin intervention efficacy:

- 1. Restricting the availability of tobacco and opportunities for smoking
- 2. Restructuring environmental contexts
- 3. Educating and persuading young people about the harms of smoking and social norms via multiple methods and communication channels
- 4. Modelling social/situational resistance skills

The intervention, which is to be to be evaluated in the proposed study, has been developed by ASH Wales in collaboration with the investigator team and integrates these evidenceinformed techniques and functions within a multi-level smoking prevention for FE settings.

4.2 Rationale for current trial

Preventing youth smoking is a priority for all UK governments and public health agencies. New universal interventions that can deliver further reductions in youth smoking are required to maintain recent decreases in smoking and address social inequalities in health outcomes. However, at present, there are no evidence-based smoking prevention interventions for FE settings and the feasibility and acceptability of using a cluster RCT design in such settings is also uncertain.

Systematic reviews have consistently found that multi-level adolescent health improvement interventions, addressing both individual and environmental determinants of behaviour, are the most effective^{20,23,25,26}. Interventions which include 'higher-level' environmental components also tend to be more cost-effective²⁷ and less likely to generate inequalities than individually focused components alone^{22,29}. However, if interventions are to deliver major public health gains they must have sufficient reach and be feasible to deliver and sustain³⁰.

This study will evaluate a multi-level intervention that balances the need for standardised evidence-informed inputs and processes with some flexibility to allow for local adaption to support universal adoption, institutional ownership and sustainable implementation of multiple activities^{31,32}. Informed by the socio-ecological model of health behaviour³³ and recent systematic reviews of effective smoking prevention methods and approaches²⁰⁻²⁴, the intervention logic model and design have been co-produced by staff at ASH Wales and the research team in consultation with Public Health Wales, the ALPHA youth group and FE staff.

Prior to undertaking a study to evaluate the effectiveness of this intervention, a pilot trial and process evaluation are required to discover whether the intervention is feasible and acceptable to implement across a range of FE settings ^{34,35}. Furthermore, there may be challenges to using a trial design and collecting data in FE settings. To address this uncertainty, the proposed study also aims to evaluate the feasibility and acceptability of the trial design and methods across a range of FE settings.

4.3. Risk and Benefits

No participant is likely to be subjected to any physical or psychological risks in relation to the intervention or their participation in the research study.

FE settings participating in the evaluation will facilitate collection of data from students and there will be a very limited degree of disruption for some staff and students. However, we propose to adapt strategies this team has used for collecting data in recent pilot and phase-III cluster RCTs of schools, which have minimised disruption and been successful in ensuring a high response and retention rate^{e.g.36,37-39.} For example, the trial manager will work with each participating FE setting to identify the most convenient time and place for students to complete baseline and follow-up e-surveys on-site, and for students and staff to participate in focus groups. It will also be made clear that participation is voluntary and participants can withdraw at any point. Any potential for harmful effects due to the intervention will be explored via the process evaluation.

After the follow-up surveys, saliva samples will be collected for cotinine and anabasine testing from 192 students to examine the validity of self-reported smoking measures, and if under/over-reporting varies by arm, using a non-invasive technique which has been used by the applicants in other studies with children and adolescents (e.g. ASSIST³⁶; CHETS ⁴⁰; the Strengthening Families Programme RCT).

There is potential for major public health benefits via the prevention of smoking at this key transitional stage in the life-course. We expect participants in the intervention arm to

experience benefits in terms of reduced smoking. A pilot trial and process evaluation are required first to examine acceptability, feasibility and potential impacts prior to any larger, more expensive, phase-III evaluation³⁴. By undertaking this pilot trial during the 2014-15 academic year, the intervention costs will be supported entirely by existing Big Lottery funding provided to ASH Wales for The Filter youth project. The research team also benefit from UKCRC centre of excellence funding for the Centre for the Development and Evaluation of Complex Interventions for Public Health Improvement (DECIPHer), including support and knowledge exchange staff.

5 Trial objectives

5.1 Primary objective

This study will evaluate the feasibility and acceptability of implementing and trialling 'The Filter FE Challenge', which is a universal, multi-level smoking prevention intervention for 16-18 year olds in general FE colleges and 'sixth form' colleges attached to secondary schools.

The first objective is to assess whether pre-specified feasibility and acceptability criteria relating to the intervention and trial design are met sufficiently for progression to a larger, phase-III effectiveness trial. To meet this primary objective the following research questions will be addressed:

- Did the intervention activities occur as planned in (at least) two out of three intervention settings?;
- Were the intervention activities delivered with high fidelity across all settings?;
- Was the intervention acceptable to the majority of FE managers, staff, students and the intervention delivery team?;
- Was randomization acceptable to FE managers?;
- Did (at least) two out of three colleges from each of the intervention and control arms continue to participate in the study at 1-year follow-up?;
- Do student survey response rates suggest that we could recruit and retain at least 70% of new students in both arms in a subsequent effectiveness trial?

The specific, detailed 'progression criteria' via which these research questions will be assessed are detailed in **section 14.1**. These criteria will be considered by the TSC. It is important that some discretion is applied in judging whether these criteria have been met, as some of these, such as a college dropping out due to change in management, are not necessarily under the control of the research team.

5.2 Secondary objectives

The second objective is to explore the experiences of FE students, staff and the intervention delivery team, with the aim of aiding refinement of the intervention and study design prior to a potential phase-III trial. With this intent the following questions will be explored:

- What are students, college staff and intervention team members' experiences of the intervention and views about its' potential impacts(s) on health?
- What are the barriers and facilitators to implementation and how do these vary according to college context and/or other factors?
- Were there any unexpected consequences?
- How acceptable were the data collection methods to students and staff and do participants think longer term follow-up via email or phone interview would be feasible?
- What resources and partnerships are necessary for a phase-III trial?

The third objective is to pilot primary, secondary and intermediate outcome measures and economic evaluation methods prior to a potential phase-III trial. With this aim student survey data will be collected and analysed to answer the following questions:

- Does the primary outcome measure (smoking weekly or more) have an acceptable completion rate, adequate validity and minimise floor/ceiling effects?
- Do cotinine concentrations of saliva samples indicate any evidence of response bias between arms in self-reported smoking status?
- Was it feasible and acceptable to measure all the secondary and intermediate outcomes of interest at baseline and follow-up?
- Is it feasible to assess cost effectiveness using a cost utility analysis within a phase III trial?

6 Trial design

The project is a pilot cluster randomised controlled trial with FE institutions as the unit of randomisation. The embedded process evaluation will utilise a quantitative survey, observational and qualitative (focus group and interviews) methods.

7 FE institution selection

Six FE settings in south Wales will be purposively sampled for a pilot trial to examine delivery and trial methods in a range of institutional contexts. The following diversity/matching criteria will be used to recruit six FE Settings: 'sixth form' colleges attached to schools (n=2); small FE colleges/campuses (new intake fewer than 500) (n=2); large FE colleges/campuses (new intake more than 500) (n=2).

7.1 Exclusion criteria

To avoid contexts where implementation may be less challenging, private institutions, small sites (with fewer than 100 students) and 'sixth forms' at schools where fewer than 10% of students are entitled to free school meals (FSM) will not be included in this study. These studies would be eligible to participate in a subsequent evaluation of effectiveness.

FE institutions where ASH Wales have developed and piloted educational materials will be excluded from this study and subsequent phases of evaluation.

To minimise the potential for contamination across arms in any subsequent evaluation of effectiveness no more than one FE setting would be recruited from any Middle Layer Super Output Area (MSOA) nor will FE settings be recruited in neighbouring MSOAs. This would ensure a significant 'buffer zone' while not being so restrictive as to constrain recruitment. However, these criteria will not be applied in this study as the aim here is to examine intervention feasibility and acceptability rather than effectiveness.

8 Participant selection

Students are eligible for selection if they are aged between 16 and 18 years old and begin further education studies in one of the participant institutions in September 2014. Students who report being older or younger that 16-18 will be excluded from our analyses. All staff and students at the intervention settings are eligible for (purposive) selection into the focus groups. Staff undertaking the staff training intervention component will be asked to complete brief survey post-training. FE managers and The Filter intervention team will be recruited to post-intervention interviews.

9 Outcome measures

9.1 Primary outcome measure/s

The pilot primary outcome is regular smoking (defined as smoking at least one cigarette weekly or more) and is measured within baseline and follow-up surveys. This study will examine prevalence, completion rate and validity of this measure. A validation sub-study⁴³ will compare the self-reported smoking measure against the results of cotinine and anabasine testing saliva samples from a sub-sample of students. A subsequent effectiveness trial would compare smoking rates between the intervention and control groups at follow-up, adjusting for baseline values, with additional sub-group analysis conducted by baseline smoking status to assess if there is an intervention effect among baseline non-smokers (intervention prevents uptake) and among baseline smokers (intervention promotes cessation).

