5. Youth work activities. To educate and persuade students about the harms of smoking and model social/situational resistance skills, qualified youth workers will work with college staff and students to plan and deliver a range of youth work activities on-site. Youth workers will launch the project in the autumn term, and then work with staff and/or student groups to identify 5, 10 or 15 groups (depending on institutional size) of 10-20 students to take part in locally tailored group-based activities. These group-based youth work activities will be provided on-site during college-time. As with the staff training, the numbers of sessions delivered varies according to the FE setting's size to ensure resources are distributed appropriately: five two-hour sessions will be provided at smaller 'sixth form' sites; ten and fifteen two-hour sessions will be provided at the medium and large general FE settings respectively. Students will not be targeted based on their smoking status or any other characteristics as the aim is to recruit as many newly enrolled students as possible. Information about online support/advice services will also be provided to current smokers. Youth workers are trained to use 'graffiti walls' and/or other arts-based activities where appropriate and will also publicise the annual Cut Films competition (an anti-tobacco short films competition for young people).

In this study, the intervention will be managed and delivered directly by the ASH Wales inhouse staff team working on The Filter youth project.

Control group

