As a pilot trial, the proposed study is not powered to provide a definitive comparison between intervention and control groups and as such p-values will not be presented. The reliability and validity of the pilot primary, secondary and immediate outcome measures will be assessed via: analyses of completion rates for each measure (total score and each item), overall and by gender and SES; calculating mean scores, standard deviations and response distributions to examine potential 'floor'/'ceiling' effects; calculating intra-class correlations for each measure to examine the stability of measures over time; and, Cronbach's alpha statistics (baseline and follow-up) to assess the internal consistency of measures. Self-reported smoking will be validated though cotinine and anabasine testing of saliva samples to examine reporting bias and assess variation across arms. We will assess this by estimating the mean difference and 95% confidence interval (CI) for the difference in cotinine values between self-reported smokers and non-smokers in the intervention and control arms. If these 95% CI overlap this would suggest that levels of misreporting did not differ significantly between arms.

Estimating attrition is important as it will inform the degree to which any sample size calculation needs to be increased to account for attrition in a subsequent larger trial. At an individual-level, we will firstly compare the baseline characteristics of those who remain in the study and provide primary outcome data to those who drop-out. To do this we will examine levels of attrition by study arm, gender, ethnicity, socio-economic status, baseline smoking status (overall and by arm) and whether participants were still registered as attending the college at the 1-year follow-up. Following guidance issued on how to deal with missing data in clinical trials⁵⁰⁻⁵² and the strategy implemented in a highly-cited smoking cessation trial⁵³, we will then run a series of sensitivity analyses to estimate the potential effects of missing data. For the primary analysis we will use multiple imputation to attempt to correct for any potential bias caused by missing data^{54,55}. This will include the observed predictors of smoking status and loss to follow-up to impute missing outcome data. At a minimum, 20 imputed datasets will initially be generated, and point estimates combined with

FILTER PROTOCOL

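### The mean cotinine difference used to judge misreporting by arm also moves with honest light or occasional smoking, and anabasine has no role in it

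*Protocol*

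**What the plan says.** The pilot primary outcome in protocol section 9.1 is "regular smoking (defined as smoking at least one cigarette weekly or more". The same section says a validation sub-study "will compare the self-reported smoking measure against the results of cotinine and anabasine testing saliva samples". Section 4.3 gives the purpose as checking validity and "if under/over-reporting varies by arm"; sections 10.6 and 14.3a give the same aim.

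The research question in section 5.2 is "Do cotinine concentrations of saliva samples indicate any evidence of response bias between arms in self-reported smoking status".

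Section 15 opens with both markers: "Self-reported smoking will be validated though cotinine and anabasine testing of saliva samples to examine reporting bias". The method it then gives is the mean "difference in cotinine values between self-reported smokers and non-smokers in the intervention and control arms", with a 95% confidence interval for each arm. Overlap of the two intervals is taken to mean that misreporting was similar.

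Both assays are named in the synopsis and in sections 3.2, 4.3, 9.1, 10.2 and 15. Cotinine alone is named in the section 5.2 question, in sections 10.1, 10.6 and 14.2, and in the section 15 contrast. No section says how an anabasine result changes any conclusion.

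**The concern.** The self-report is a yes/no frequency category. The statistic is the difference between two mean concentrations, and section 15 reads it as a level of misreporting. A mean concentration depends on amount smoked as well as on who answered truthfully. The difference shrinks if declared non-smokers conceal smoking. It also shrinks if truthful weekly smokers smoke less, or if more truthful non-weekly students smoke now and then.

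These quantities need not be equal across arms. Section 4.3 anticipates reduced smoking among intervention students, and section 9.2 pilots cigarettes per week as an outcome for baseline smokers. If the intervention leads weekly smokers to cut down, their mean cotinine falls and the arm looks as though it under-reports more. If it reduces occasional smoking, or mainly the lightest weekly smokers stop, the difference widens and real under-reporting is hidden.

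The answer feeds a stated secondary objective: whether the primary outcome intended for phase III is valid and reported alike in both arms.

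**Working it through.** **Sample.** The amendment history gives 32 students per setting. 6 x 32 = 192, which reproduces the stated size; 3 x 32 = 96 per arm. (Section 10.1 still says 200; that is a separate point to reconcile.)

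**Model with no misreporting.** The documents give no cut-off, prevalence or marker level, so the inputs below are assumptions shown as ranges. The one premise is that cotinine rises with amount smoked or with other nicotine intake. Scale the mean of ordinary weekly smokers to 1, and let:
- g = share of truthful weekly smokers who are light, at relative level v;
- f = share of truthful non-weekly students with some exposure, at relative level u.

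Within-arm difference: D = 1 - g(1 - v) - f x u.

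For comparison, take g = 0, f = 0 and a share m of declared non-smokers who are concealed ordinary weekly smokers: D = 1 - m. A shortfall of f x u is therefore indistinguishable from m = f x u.

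**Within one arm**
- f = 5%, u = 0.1: f x u = 0.005, the same as 0.5% concealment.
- f = 10%, u = 0.5: 0.05, the same as 5%.
- f = 20%, u = 1.0: 0.20, the same as 20%.
- g = 20%, v = 0.1, f = 0: D = 1 - 0.20 x 0.9 = 0.82.
- g = 50%, v = 0.1, f = 0: D = 1 - 0.50 x 0.9 = 0.55.

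**Between arms.** With the same u and v in both arms, D(intervention) - D(control) = -(difference in g)(1 - v) - (difference in f) x u. Equal g and f give zero. Otherwise:
- g of 50% in intervention v 20% in control, v = 0.1: -0.30 x 0.9 = -0.27. This looks like more under-reporting, although it is only lighter smoking.
- f of 20% v 5%: -0.15u, that is -0.015 to -0.15 for u from 0.1 to 1.0.
- f of 5% v 20%: +0.015 to +0.15. This would offset a true excess of concealment of 1.5 to 15 percentage points in the intervention arm.

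**If the split is not weekly v not weekly.** Section 15 does not define its two groups. If occasional smokers are counted as smokers, they move from the f term to the g term with a low v. D still falls without any misreporting.

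**Would the interval rule react?** Assume the sample mirrors the population, weekly smoking is 10-30%, the SD among smokers equals their mean, f = 10% and u = 0.5 (SD among the exposed also equal to their mean), and ignore clustering. Self-reported weekly smokers per arm: 96 x 0.10 = 9.6 to 96 x 0.30 = 28.8. Non-smoker variance: 2 x 0.1 x 0.25 - 0.05^2 = 0.0475. At 20%: SE = sqrt(1/19.2 + 0.0475/76.8) = 0.230, half-width 0.45, so the arms must differ by 0.90 before the intervals separate. The figures at 10% and 30% are 1.27 and 0.74. A gap of 0.27 would not be flagged.

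**The case against.** The strongest reply is that the protocol names two markers and that cut-offs, classification and laboratory rules belong in a statistical analysis plan. That stands for the numerical cut-off and for assay detail. It does not rescue the contrast, because section 15 itself fixes both the statistic and its interpretation.

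A reader might infer more than the documents support:
- *That truthful occasional or light smokers are labelled misreporters.* Section 15 compares arm means. It sets no cut-off and classifies no student, so counts of falsely labelled students would describe an analysis that is not planned.
- *That the sub-study relies on one marker of nicotine from any source.* Sections 9.1 and 15 name anabasine as well. The defect is only that it has no role in the contrast or the section 5.2 question.
- *That nicotine-product use will differ by arm.* Section 12 says "Information about online support/advice services will also be provided to current smokers", but the intervention description mentions neither nicotine replacement nor e-cigarettes. This route is speculative; the argument from amount smoked does not need it.
- *That saliva results decide progression.* No criterion in section 14.1 rests on them, and section 15 lists other checks of reliability and validity.

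It is also fair that exposure equal in both arms largely cancels and that the pilot is not powered. With intervals this wide, a falsely flagged difference is unlikely. The likelier errors are false reassurance, over-reading the point estimates, and carrying the same contrast into phase III.

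**Conclusion.** The point holds in limited form. The section 15 contrast cannot separate misreporting from truthful light or occasional smoking, or from other nicotine exposure, and the intervention is expected to change at least the amount smoked. With zero misreporting, plausible but assumed inputs lower the within-arm difference by 0.005-0.20 through exposed non-weekly students, and bring it to 0.82-0.55 through light weekly smokers. A between-arm gap arises only if these shares or levels differ by arm; the example above gives -0.27. Anabasine is assayed without a stated use.

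The conclusion rests on cotinine rising with intake and on the section 15 groups being split by current self-reported smoking. It does not rest on any half-life or detection window, which the documents do not give. It affects a secondary objective of a pilot, not its progression criteria.

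**What to change.** In sections 5.2, 9.1, 14.2 and 15:

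1. Replace the mean-cotinine-difference reading with the proportion, by arm and with an interval, of students who report no recent tobacco use but are above a pre-set marker cut-off. The value can be set in the analysis plan before the assays are read.
2. Show never, less-than-weekly and weekly smokers separately.
3. State that anabasine is used to judge tobacco use in cotinine-positive self-reported non-smokers. This assumes it marks tobacco rather than nicotine products, which the protocol should say and support.
4. At saliva collection, ask a few questions on last cigarette and recent nicotine-product use. These answers cannot be recovered reliably later.
5. Draw no over-reporting conclusion from marker-negative light weekly smokers. Purely as an assumption, if one cigarette is detectable for 1-3 days, a student smoking one a week and tested on a random day is missed 4/7 to 6/7 of the time (57-86%).
6. State that saliva tests recent exposure, not the weekly threshold.

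The cost is a short form for 192 students and revised wording; both assays are already planned. The downside is a smaller denominator for under-reporting. With 10-30% weekly smoking and 5-20% of the rest set aside, it runs from 96 x 0.70 x 0.80 = 54 to 96 x 0.90 x 0.95 = 82 students per arm, so the proportion will be imprecise and should be reported as such.
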